Part I, Aim 1. Older adults obtaining primary care via Atrium Health Wake Forest Baptist (AHWFB) will participate in a comprehensive sleep health assessment. This two-part, in-person visit will consist of validated sleep-health assessments, objective sleep-activity monitoring (via sleep watch (e.g., Fitbit) and daily diary), and a subset of physical performance measures. At the conclusion of the second visit, older adults will be asked to respond to a brief set of open-ended questions on treatment preferences. We plan to enroll up 40 older adults in this aim. Eligibility criteria is described below.

Part II, Aim 2. A one-arm, non-randomized pilot study will be conducted using a successive cohort design. Each cohort will include four to six participants. All participants will receive the intervention in a group setting. After each cohort, the study team will review intervention session notes and other study materials to determine whether what, if any, refinements should be made to the intervention content or study procedures. Participants will be older adults who are currently receiving primary care at AHWFB, meet criteria for poor sleep and low activity, and live within the greater Winston-Salem region. Specific inclusion and exclusion criteria are described below.

The intervention includes a four-session, in-person program delivered by a Master's-level provider. All participants will complete a sleep-health assessment before the intervention identical to Part I, Aim 1 (*NOTE: If a participant was enrolled and completed Aim1 assessments, only select assessments will be collected during the pre-intervention assessment, including the Insomnia Severity Index, sleep watch, and a sleep-activity diary. These materials may be sent to the participant via postal mail prior to session 1.*) Prior to enrollment, study staff will review each participant's sleep-health assessment, daily diary and actigraph (if applicable). This review will help to evaluate a participant's "fit" for the intervention (i.e., no unaddressed health concerns that may negatively limit participation in the group-based intervention).

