Sleep watch and daily diary Three to five days of continuous daytime and nighttime sleep watch monitoring ³⁶ plus daily sleep-activity diary ³⁷ (Wake-up prompts: sleep-wake schedule, nighttime awakenings, overall sleep quality. Morning, Midday, Afternoon/Evening, & Bedtime prompts: daytime activity, sedentary time, mood, pain, fatigue levels)	Functional assessment Functional performance tests: Short Performance Physical Battery (SPPB) ⁷

Intervention Aim (Treatment):

Part II, Aim 2 (Sleep Health Education Program). A one-arm, non-randomized pilot study will be conducted using a successive cohort design. Each cohort will include four to six participants . Participants will be older adults who are currently receiving primary care at AHWFB, meet criteria for poor sleep and low activity, and live within the greater Winston-Salem region. Specific inclusion and exclusion criteria are described below. All participants will receive the intervention in a small-group setting. Group sessions will be conducted in-person or virtually. Participants will complete pre- and post-program assessments in addition to daily sleep-activity diaries throughout the course of the intervention. Note: all assessments will be identical to those used in Aim 1 – if a participant has completed Aim 1, an abbreviated assessment will be administered to include the Insomnia Severity Index and a daily sleep diary. The intervention includes a four-session program delivered by a Master's-level provider. Each session will be approximately 30-45 minutes in length. Each session will include education and coaching on developing healthy nighttime sleep and daytime activity behaviors. At the end of each session, the Interventionist will complete a detailed Session Note that will track material covered, personalized recommendations, and any questions asked. All participants will complete a post-intervention assessment (including select assessments: SF-12, Geriatric Pain Measure, PHQ-9, Pittsburgh Sleep Quality Index, Insomnia Severity Index, Epworth Sleepiness Scale, Flinders Fatigue Scale). Participants will also be asked to provide feedback on their experience receiving

SWELL. After each cohort, the study team will review intervention session notes and study assessments to determine whether what, if any, refinements should be made to the intervention content or study procedures.

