The behavioral intervention is based on the Principal Investigator's prior work developing and testing an evidence-based behavioral sleep intervention for older adults.⁸ In short, the prior intervention focused solely on improving nighttime sleep problems. An overview of the proposed content is provided below. Final content, including daytime activity components of the intervention, will be refined during the course of the study (based on Aims 1 and 2 findings and feedback). Sample content is included as an attachment to this application.

Visit	Timing	Activities	Data Collection	Time Required
Baseline	Week 0 (Visit 1)	Pre-Intervention Assessment	Quantitative assessments, sleep watch, and sleep-activity diary Note: Assessments identical to those described in Aim 1.*	60 minutes
	Week 1 (Visit 2)		*If participant completed Aim 1, Visit 1 and 2 will be collapsed and only select questionnaires will be administered (see abbreviated pre-program assessment attached).	
Session 1	Week 2	SWELL24 Session 1 Sleep and activity: Understanding a 24 hour cycle	Sleep-activity diary	30 minutes
Session 2	Week 3	SWELL24 Session 2 Following a regular sleep-wake schedule, including tips for daytime engagement	Sleep-activity diary	30 minutes
Session 3	Week 4	SWELL24 Session 3 Optimizing daytime routines and activities	Sleep-activity diary	30 minutes
Session 4	Week 5	SWELL24 Session 4 Relapse prevention and long-term strategies	Sleep-activity diary Give sleep watch and sleep diary to return at post-intervention assessment.	30 minutes
Post-Treatment	Week 6	Post-Intervention Assessment	Quantitative assessments, review sleep watch and sleep-activity diary. Note: Select assessments administered in Aim 2: SF-12, Geriatric Pain Measure, PHQ-9, Pittsburgh Sleep Quality Index, Insomnia Severity Index, Epworth Sleepiness Scale, Flinders Fatigue Scale. At the end of the visit, participants will also be asked to provide feedback on their experience receiving SWELL24.	60 minutes

Outcome Measure(s)

Primary outcome: sleep efficiency (per sleep watch)

Secondary outcome: total daytime activity (per sleep watch); insomnia severity (per self-reported Insomnia Severity Index); daytime consequences (per self-reported assessment, daily diary)

Analytical Plan

Aim 1: Sleep-Health Assessment

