***For participants enrolling in the pilot trial (Aim 2) who have also completed Aim 1:**

- The consent visit for Aim 2 *may* be completed virtually via REDCap through an online survey platform which can be accessed on a computer, mobile phone, or tablet. A virtual visit will be scheduled with a research staff member using a secure platform (e.g., Webex). The participant will be able to open the survey link during the visit, read and review the document with the research staff. When they get to the bottom of the document, they will be able to sign their name if they agree to participate. The REDCap eConsent Framework adds an extra certification page to the end of the survey with a read-only PDF copy of the informed consent document; they will be asked to confirm that all of the information in the document is correct and that by signing the form electronically, it is the equivalent of signing a physical document. The participant will receive a PDF copy of the signed informed consent. The survey responses will be stored in a REDCap project that is separate from any de-identified participant data. *If the consent visit is completed virtually, then the pre-program assessment (Insomnia Severity Index) may be shared with the participant via an electronic REDCap survey during after consent has been obtained.*

Confidentiality and Privacy

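### For Aim 2 participants who already completed Aim 1, the protocol conflicts on whether the sleep watch is in the shortened baseline, no section names the PSQI in it, and the SAP does not say which value is the baseline.

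*Protocol*

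**What the plan says.** The protocol's Subject Recruitment Methods section allows people who finished the Aim 1 assessment to enter the Aim 2 pilot. Four places in the protocol bear on their shortened pre-intervention assessment:

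- **Design, Part II, Aim 2:** "only select assessments will be collected during the pre-intervention assessment, including the Insomnia Severity Index, sleep watch, and a sleep-activity diary". It adds: "These materials may be sent to the participant via postal mail prior to session 1".
- **Interventions and Interactions, Part II, Aim 2:** "if a participant has completed Aim 1, an abbreviated assessment will be administered to include the Insomnia Severity Index and a daily sleep diary". The watch is not listed.
- **Visit table, Baseline row:** the general entry is "Quantitative assessments, sleep watch, and sleep-activity diary Note: Assessments identical to those described in Aim 1". For Aim 1 completers, an asterisk says "Visit 1 and 2 will be collapsed and only select questionnaires will be administered (see abbreviated pre-program assessment attached". It names no instrument.
- **Informed Consent, virtual route for Aim 1 completers:** "the pre-program assessment (Insomnia Severity Index) may be shared with the participant via an electronic REDCap survey".

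At Week 6 the visit table has everyone return the watch and diary and complete seven questionnaires; the entry begins "Select assessments administered in Aim 2: SF-12, Geriatric Pain Measure, PHQ-9, Pittsburgh Sleep Quality Index, Insomnia Severity Index". Under Outcome Measure(s), the primary outcome is sleep efficiency from the watch. One secondary outcome is "daytime consequences (per self-reported assessment, daily diary".

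Under Response to intervention, the SAP examines percent change over the intervention period in four measures: Fitbit sleep efficiency, Fitbit daily steps, the ISI, and PSQI daytime dysfunction. It does not say which pre-intervention value is the baseline for any of them.

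**The concern.** A percent change needs a starting value. For participants new to the study there is only one, because their baseline is the full Aim 1 battery in Weeks 0 and 1. Aim 1 completers may have two candidates, an Aim 1 value and a fresh one, or only the Aim 1 value if the measure is not repeated.

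The pilot has one arm, and the protocol's Analytical Plan says it is looking for any signal of a treatment effect. With no comparison group, change between the Aim 1 assessment and Session 1 cannot be separated from change during the program. Pooling participants whose change starts shortly before Session 1 with others whose change starts at an unknown earlier date would mix two quantities in one summary. It would also weaken the SAP's stated purpose, which is to judge whether the measures are sensitive to change over the intervention period.

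**Working it through.** No figure in the plan needs reproducing. The check sets each description of the shortened baseline against the four SAP change measures.

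| Source (Aim 1 completers) | Watch: sleep efficiency, steps | ISI | PSQI | SAP measures with a named current baseline |
|---|---|---|---|---|
| Design | named | named | not named | 3 of 4 |
| Interventions and Interactions | not listed | named | not named | 1 of 4 |
| Visit table, asterisk | only questionnaires are shortened, so the watch arguably stays | deferred to form | deferred to form | cannot be determined |
| Informed Consent, virtual route | outside its scope (electronic questionnaire) | named | not named | not a full list |

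New participants have all 4 measures at baseline and at Week 6.

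**Where the sections conflict.** Only Design and Interventions and Interactions disagree as lists, and they disagree on the watch. The visit table names no instrument for this subgroup, so it contradicts neither. The consent passage covers what may be sent electronically, and a watch cannot be sent that way.

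**PSQI.** It is named in 0 of the 4 places. Of the seven Week 6 questionnaires (SF-12, Geriatric Pain Measure, PHQ-9, PSQI, ISI, Epworth, Flinders), only the ISI is named in the shortened baseline. Of the other six, only the PSQI is among the SAP's percent-change measures, so it is the one omission that affects the planned analysis.

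**Interval from baseline to Week 6 for the PSQI.**

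- New participants: the PSQI belongs to Visit 2 (Week 1), so 6 − 1 = 5 weeks.
- Aim 1 completers, PSQI repeated at the collapsed Week 0–1 visit: 6 − 1 = 5 to 6 − 0 = 6 weeks.
- Aim 1 completers, Aim 1 value used: not stated. Some lag is to be expected, because the Objectives say the intervention is to be informed by Part I data.

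**Why the choice matters.** With the usual definition (the SAP gives no formula), percent change = 100 × (Week 6 − baseline) / baseline. If the baseline is the Aim 1 value, the numerator splits as

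Week 6 − Aim 1 = (Week 6 − value just before Session 1) + (value just before Session 1 − Aim 1).

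The second bracket is drift before the intervention. It enters the reported change, and a one-arm design has nothing to subtract it with.

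**How many.** The Sample Size section allows up to 12 in Aim 2. The number who completed Aim 1 is not given, so 0 to 12 could be affected; with 0 there is no effect.

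**The case against.** The strongest reply is that the questionnaire content is fixed by the attached form, which is not public. The lists in Design and in Interventions and Interactions are worded as open, so the form may well contain the PSQI. This stands. A reader might infer that the PSQI is not collected before the intervention in these participants; the documents do not support that. They show only that no section names it.

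A reader might also infer four mutually contradictory descriptions. As set out above, there is one real conflict, over the watch.

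Nor are daytime consequences left without any current baseline. The protocol also measures them by diary, Design and Interventions and Interactions both name a pre-intervention diary for this subgroup, and the SAP reviews diaries qualitatively for signals of change. The PSQI is the only percent-change measure of daytime dysfunction, but not the only evidence.

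It is fair to add that every baseline precedes Session 1 and that uncontrolled drift affects all participants in a single-arm study; this subgroup differs in degree. It would be tempting to put a size on the resulting bias. The documents give neither the number of Aim 1 completers nor any information on change between the two assessments, so no figure can be defended.

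Finally, this is a small pilot that is not powered for efficacy. That limits the consequence but does not answer the point, which concerns what the reported change means rather than its precision.

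**Conclusion.** The point holds in a limited form. Design and Interventions and Interactions conflict on whether the watch, the source of the primary outcome and of steps, is in the shortened baseline. Separately, the PSQI is unnamed in that baseline while the SAP analyses its change from an undefined starting value.

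The consequence is conditional. If the lists are followed as written, PSQI change for Aim 1 completers is missing or starts from an Aim 1 value of unstated age. Under the Interventions and Interactions list, the same applies to both watch measures. If the form already contains the PSQI and the Design section governs the watch, sleep efficiency, steps, ISI and PSQI all have a current baseline, and only the wording and one SAP sentence need repair.

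Severity is minor to should-fix, depending on the unseen form and on how many of the up to 12 participants completed Aim 1.

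**What to change.** **Protocol.** Make Design, Interventions and Interactions, the visit table, the virtual-consent text and the attached form agree that the shortened Aim 2 baseline comprises the ISI, PSQI, sleep watch and diary, collected before Session 1. The routes already allowed are enough: post (Design) and electronic survey (Informed Consent). The watch should go out after consent and early enough for the three to five days of wear described for Aim 1.

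**SAP.** State that this value, not the Aim 1 value, is the baseline for each percent change, and report how many participants were Aim 1 completers.

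**If baselines are already collected.** The SAP is dated 10/17/2025 and the protocol version 05.02.2024, so this is possible, though the documents do not say. In that case, state which value was used for each measure, its age at Session 1, and how many participants were Aim 1 completers.

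**Cost.** Wording changes in four places in the protocol, a check of the form, and one or two SAP sentences. The downside is one extra short questionnaire for this subgroup, with no extra visit. If data collection is over, only the SAP disclosure is needed.

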***For participants enrolling in the pilot trial (Aim 2) who have also completed Aim 1:**

- The consent visit for Aim 2 *may* be completed virtually via REDCap through an online survey platform which can be accessed on a computer, mobile phone, or tablet. A virtual visit will be scheduled with a research staff member using a secure platform (e.g., Webex). The participant will be able to open the survey link during the visit, read and review the document with the research staff. When they get to the bottom of the document, they will be able to sign their name if they agree to participate. The REDCap eConsent Framework adds an extra certification page to the end of the survey with a read-only PDF copy of the informed consent document; they will be asked to confirm that all of the information in the document is correct and that by signing the form electronically, it is the equivalent of signing a physical document. The participant will receive a PDF copy of the signed informed consent. The survey responses will be stored in a REDCap project that is separate from any de-identified participant data. *If the consent visit is completed virtually, then the pre-program assessment (Insomnia Severity Index) may be shared with the participant via an electronic REDCap survey during after consent has been obtained.*

Confidentiality and Privacy

Confidentiality will be protected by collecting only information needed to assess study outcomes, minimizing to the fullest extent possible the collection of any information that could directly identify subjects, and maintaining all study information in a secure manner. To help ensure subject privacy and confidentiality, only a unique study identifier will appear on the data collection form. Any collected patient identifying information corresponding to the unique study identifier will be maintained on a linkage file, stored separately from the data. The linkage file will be kept secure, with access limited to designated study personnel. Following data collection subject identifying information will be destroyed six years after the closure of the study. All identifying information will be physically destroyed. All remaining research records will be de-identified, consistent with data validation and study design, producing an anonymous analytical data set. Data access will be limited to study staff. Data and records will be kept locked and secured, with any electronic data password protected. No reference to any individual participant will appear in reports, presentations, or publications that may arise from the study.

Data and Safety Monitoring

The principal investigator will be responsible for the overall monitoring of the data and safety of study participants. The principal investigator will be assisted by other members of the study staff.

Reporting of Unanticipated Problems, Adverse Events or Deviations

Any unanticipated problems, serious and unexpected adverse events, deviations or protocol changes will be promptly reported by the principal investigator or designated member of the research team to the IRB and sponsor or appropriate government agency if appropriate.

Official Title: Sleep Well 24 (SWELL24): Promoting Healthy Sleep-wake Behaviors Across a 24-hour Cycle in Frail Older Adults
NCT05780983
10/17/2025

SWELL24 (PI: [name])
Pilot Feasibility Trial
Analysis Plan

In preparation for a larger trial, we will collect the following: *Retention rate*. This will be defined as the number of participants who complete all intervention sessions out of the total number enrolled. *Adherence to personalized recommendations*. Adherence to personalized behavioral recommendations is a key measure of acceptability. This information will be gathered through process notes recorded after each intervention session and in sleep and activity diaries completed on a daily basis during the course of the intervention. *Response to intervention*: In order to determine dose, sequencing, and timing of intervention components to be used in a larger trial, participants will report daily sleep-wake behaviors using a daily diary. This information will be reviewed qualitatively for potential signals of change. In preparation for a full trial, we will evaluate whether selected measures are sensitive to change over the intervention period. This will include examining percent change in both objective and subjective sleep-activity measures. Specifically, this will include changes in objective sleep efficiency (Fitbit: sleep efficiency) and activity levels (Fitbit: total daily steps) in addition to self-reported insomnia severity (Insomnia Severity Index) and daytime dysfunction resulting from poor sleep (Pittsburgh Sleep Quality Index, 3-component scoring).
